6.1.4.3. Reasons for early termination of subjects

Possible reasons for early termination may include, but are not limited to the following:

1. Withdrawal of informed consent form (ICF): The subject decides to withdraw from the study. This decision must be “independent decision” and should be documented in the subject study file;
2. Investigator's discretion: The investigator may choose to withdraw a subject from the study if there are safety concerns;
3. Adverse events (aEs): AE or SAE may lead to subject discontinuation from the study. If the investigator decides to discontinue a subject from

the study, this subject must be followed up until the AE is resolved or until the stable clinical endpoint is reached;

4. Death (if applicable);
5. Loss to follow-up: All subjects should return to participate in all scheduled clinical follow-ups, providing the appropriate contact information in order to complete the specified (telephone) follow-up. Every attempt will be made to have all subjects complete the follow-up visit schedule. A subject will not be considered lost to follow-up until the last study visit. If a subject can't return for mandatory clinical visits, 3 telephone calls should be made to attempt to contact the subject to return to clinics and/or obtain safety information. Each attempt to contact should be recorded in the source document. If the subject does not respond to 3 telephone calls, the investigator must send a registered mail or the EMS which can record the mode of sending and receiving to the subject. If the subject makes no response to the registered mail or EMS which can record the mode of sending and receiving and makes no further contact, this subject should be considered to have missed the scheduled visit.
6. Termination by the sponsor.

Procedure for subject's termination in the study:

If the subject is terminated from the study before end of visit in the study, the reasons for discontinuation should be documented in the source document and kept in the study files and submitted via CRF/eCRF.

Subjects with premature discontinuation from the study will be included in the analysis set according to the definition of analysis set in the protocol; however, new subjects may not be enrolled to replace these subjects.

Criteria for sponsor's termination of the trial are as follows:

The sponsor reserves the right to temporarily suspend/terminate or prematurely discontinue the studies either at a single site, multiple sites or all sites. Reasons may include, but are not limited to safety issue, ethical issue, administrative issue, inaccurate or incomplete data record, non-compliance or unsatisfactory enrollment with respect to quality or quantity.

Procedure for sponsor's termination of the study:

If the study is prematurely terminated or suspended, the sponsor will inform all institutions of the termination or suspension and the reason(s) for the termination or suspension, in accordance with applicable regulatory requirement(s). The

investigators and EC should also be informed and provided with reason(s) for the termination or suspension by the institutions, as specified by the applicable regulatory requirement(s). The suspended study should not be resumed without the consent of the EC.

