6.1.4.8. Subject Enrollment Disposition

- Enrolled Subjects: Patients who sign the ICF and meet all eligibility criteria.
- Excluded Subjects: Subjects who are enrolled but never undergo insertion of the study catheter. Excluded subjects will be subjected to safety event reporting between ICF signature and date of exclusion. Enrolled Subjects found to be ineligible prior to insertion of the catheter are also considered as excluded.

- **Evaluable Subjects:** All enrolled subjects who have the study catheter inserted.
- **Discontinued Subjects:** Evaluable subjects but do not undergo ablation (i.e., no energy is delivered with the study catheter).
 - Discontinued subjects will remain in follow-up for 3-months post catheter insertion.
 - If an SAE is reported for a discontinued subject, the subject will be followed until event resolution (with or without sequelae), stabilization, or until the event is adequately explained.
- **Lost to Follow-up Subjects:** Evaluable subjects of which contact is lost after most recent visit (despite 3 documented attempts to contact the subject).
- **Withdrawn / Early Termination Subjects:** Subjects who withdraw consent for study participation or are withdrawn by the investigator, are terminated from the study prior to completion of all follow-up visits.
- **Completed Subjects:** Enrolled subjects who have not been excluded, discontinued, withdrawn, terminated early, or lost-to-follow-up from the study prior to the final study visit.

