- Acute Procedural Success defined as confirmation of entrance block in all clinically relevant targeted PVs after adenosine/ isoproterenol challenge. Touching up with focal catheter will be considered as acute procedural failure.
- Acute reconnection identified by adenosine/isoproterenol challenge. Among all clinically relevant targeted PVs and by subject
- Rate of PV ablation by a non-study catheter (touch-up) among all

clinically relevant targeted PVs and by subject

- Rate of repeated ablation within the 12M FU period, including timing (blanking period or after blanking) and rate of PV reconnection

6.1.5.2. Selection of method and time to evaluate, record and analyze the effectiveness parameters

- 1) Long term effectiveness will be evaluated and recorded during effectiveness evaluation period (day 91 to day 365 post index procedure) by ECG and 24h Holter at 3 months, 6 months and 12 months follow-up points. Recurrence during blanking period (day 1 to day 90 post index procedure) is not considered as long term effectiveness failure.
- 2) Acute effectiveness will be evaluated and recorded at the end of procedure by the method of adenosine/isoproterenol challenge.
- 3) All the repeated ablations will be evaluated and recorded during the study.

For the analysis of the above endpoints, see Section 7.

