AEs will be summarized, including the number of AEs and the number and percentage of subjects experiencing any AEs. All PAE, SAEs and all procedure-/device-related AEs will be analyzed in same way. The severity, relationship, AE treatment intervention, seriousness and outcome of all AEs will be described.

In addition, all AEs, PAE, serious and non-serious AEs will be summarized according to the system organ classification and preferred terms of MedDRA, and a list will be generated, including but not limited to subject identification number, age, AE term, start and end time (corresponding duration post procedure), severity, relationship, AE treatment intervention, seriousness, and outcome.

Handling of missing value

Subjects will be contacted by different means, such as by telephone, to avoid missing value.

For the primary endpoint, missing primary endpoint data of the subjects in the FAS will be excluded from the final primary effectiveness analysis as described in “Primary analysis of primary endpoint” of Section 7.5.

For those who had the investigational device inserted but not ablated, they would be replaced, and new subjects should be screened and enrolled to ensure total 110 evaluable non-roll-in subjects.

For baseline information, operational information, or secondary endpoints, all observed data will be used for analysis. Missing data imputation will not be

performed.

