2.3.5 Rules for missing data processing

In the final analysis, a sensitivity analysis for the primary endpoint, missing data will be imputed using multiple imputation.

No imputation will be performed for the missing data on baseline information, procedural information, or secondary effectiveness endpoints.

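### Withdrawal for an adverse event or safety concern also ends the rhythm follow-up that defines the primary endpoint, so ablated subjects with no recorded failure can drop out of the primary analysis

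*Protocol*

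**What the plan says.** Protocol 6.1.4.3 lists reasons for early termination of a subject. Reason 2 is investigator discretion: "The investigator may choose to withdraw a subject from the study if there are safety concerns". Reason 3 is adverse events: "AE or SAE may lead to subject discontinuation from the study". Both describe leaving the study; the section does not distinguish ending participation from ending data collection. For a subject discontinued for an AE, the only follow-up it then requires is that "this subject must be followed up until the AE is resolved or until the stable clinical endpoint is reached". Protocol 6.1.4.8 says that subjects who withdraw consent or "are withdrawn by the investigator, are terminated from the study prior to completion of all follow-up visits".

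Protocol 6.1.5.2 says long-term effectiveness is evaluated "by ECG and 24h Holter at 3 months, 6 months and 12 months follow-up points".

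On analysis, 6.1.4.3 says "Subjects with premature discontinuation from the study will be included in the analysis set according to the definition of analysis set in the protocol", and that such subjects may not be replaced. Under the missing-value heading of Protocol 7.5, "missing primary endpoint data of the subjects in the FAS will be excluded from the final primary effectiveness analysis". SAP 2.3.5 provides, as a sensitivity analysis of the primary endpoint, that "missing data will be imputed using multiple imputation". The analysis-set definitions and the detailed primary-analysis text are redacted in both documents.

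**The concern.** The ablation is given on day 0. What remains is mostly observation: visits, ECG, Holter, medication and AE collection. Withdrawing an ablated subject for an AE cannot undo delivered energy, but it does stop the rhythm monitoring from which the endpoint is read. Under the exclusion rule, a subject who leaves without a recorded failure then has no primary outcome and falls out of the denominator.

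The trial is open-label and single-arm, so no control group loses subjects in the same way. The decision to withdraw lies with the investigator. If subjects withdrawn for AEs would have failed more often than those who stayed, the observed rate is biased upwards against a fixed 50% goal. On safety, PV stenosis counts as a primary adverse event at any time in the 12-month follow-up. A subject withdrawn early for a different event is no longer seen at the visits where symptoms of stenosis would lead to imaging.

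**Working it through.** **Inputs.** SAP 1.3.3: goal 50%, assumed true rate 63%, one-sided 0.025, at least 80% power, normal approximation with the variance estimated from the observed rate, 110 evaluable, 10% attrition, 123 enrolled. Protocol 7.1: success if the one-sided lower bound exceeds 50%. The number of withdrawals for AEs or safety concerns is not given; **0 to 3 is my assumption**.

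**The plan's own figure.** n = p1(1 − p1)(z0.975 + z0.80)² / (p1 − p0)² = 0.63 × 0.37 × (1.960 + 0.842)² / 0.13² = 108.3, so 109. The stated 110 is within rounding of this, and it is the smallest n that keeps 80% power under a two-look O'Brien-Fleming boundary at half the information (final z = 1.977; 79.96% at 109, 80.3% at 110). Then 110 / 0.90 = 122.2, so 123. The design is reproduced.

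**Following the text for one subject.** Ablated; AE; withdrawn under reason 2 or 3; no failure recorded so far.
- Required afterwards under reason 3: the AE, to resolution or stability (6.1.4.3). Not required: the ECG and Holter visits (6.1.5.2).
- Disposition: terminated before all visits are complete (6.1.4.8).
- Analysis: missing primary endpoint, hence excluded (7.5).

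**How few such subjects matter.** Lower bound = p − 1.96 √(p(1 − p)/n). Each row adds back unobserved failures to the denominator.

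| Observed | Failures added back | Rate | Lower bound | Result |
|---|---|---|---|---|
| 65/110 | 0 | 59.1% | 49.9% | fail |
| 66/110 | 0 | 60.0% | 50.8% | pass (minimum count) |
| 66/111 | 1 | 59.5% | 50.3% | pass |
| 66/112 | 2 | 58.9% | 49.8% | fail |
| 67/113 | 3 | 59.3% | 50.2% | pass |
| 69/112 | 2 | 61.6% | 52.6% | pass |

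With 1.977 in place of 1.96, 66/110 gives 50.8% and 66/112 gives 49.7%, so that reversal does not depend on the interim adjustment. Within 0 to 3 withdrawals from 110 analysed, only a count of exactly 66 can be reversed. The binomial probability of exactly 66 of 110 at a true rate of 63% is about 6%.

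**Worst-case error rate.** Assume a true rate of 50% among 123 treated subjects, and that all m excluded subjects would have failed. The rate among those analysed is then 61.5/(123 − m). The chance of passing is the exact binomial tail at the smallest passing count.

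| m excluded | Analysed | Passing count | Rate among analysed | False-success risk |
|---|---|---|---|---|
| 0 | 123 | 73 | 50.0% | 2.3% |
| 1 | 122 | 72 | 50.4% | 3.5% |
| 2 | 121 | 72 | 50.8% | 3.4% |
| 3 | 120 | 71 | 51.3% | 5.0% |

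The small dip at m = 2 comes from the discreteness of the count. If withdrawal is unrelated to outcome there is no bias, only some loss of precision.

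**The case against.** Several arguments on the other side stand and limit the point.

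- **Recorded failures.** A reader might infer that any subject whose procedure went badly can be removed from the primary analysis. The documents do not support that. Acute procedural failure, use of a non-study catheter at the index procedure and post-procedure oral amiodarone are themselves endpoint failures (Protocol 6.1.5.1 a, c, g). These, and a recurrence in the evaluation period recorded before withdrawal, presumably still count. Only subjects withdrawn with no recorded failure are at issue, and nothing in the documents shows that subjects with, say, a vascular complication recur more often.
- **Exposure.** A reader might also infer that withdrawal can never reduce exposure. But 6.5.5 allows a repeat procedure, and in the blanking period PV reconnections must be ablated with the study device. The withdrawal reasons also apply between consent and the procedure, when withdrawal prevents exposure altogether.
- **Phrenic palsy.** It is tempting to say that the permanence of a palsy would go unread. A known palsy is still followed to resolution or stability (6.1.4.3, 13.2.1, 13.5). The safety gap is a later, separate event. Even there, imaging for PV stenosis is prompted by symptoms (6.5.6), not scheduled for everyone.
- **Redaction.** What counts as a missing endpoint for a partly followed subject cannot be read, so loss from the primary analysis is what the visible rule implies rather than a confirmed outcome.

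Three other defences are weaker. Keeping discontinued subjects in the analysis set does not help, because the exclusion in 7.5 acts on subjects within the FAS. Multiple imputation is a sensitivity analysis and does not change the primary test. The continued-follow-up sentence in 6.5.6 concerns early termination of the whole study, not of one subject.

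**Conclusion.** The gap is real but modest. Followed as written, the protocol allows loss of primary-endpoint data that may depend on outcome, in a design with no control group to absorb it. A later 12-month safety event in the same subject may also go undetected.

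The size rests on assumptions: 0 to 3 such withdrawals, none with a recorded failure, and, for the figures above, every one an unobserved failure. On that basis two withdrawals reverse a result only at the minimum passing count, and the false-success risk at most roughly doubles, from 2.3% to about 5% with three excluded. A reader might infer that the primary result is biased towards success. The documents show neither the direction nor the size of any bias, so these figures are upper limits within the assumed range. The point is worth acting on because the correction is short and uses visits already planned.

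**What to change.** In Protocol 6.1.4.3 and 6.1.4.8, separate ending participation from ending data collection. State that for subjects who have received ablation energy, an AE or an investigator's safety concern does not end scheduled outcome collection (ECG, 24h Holter, AE and medication data) to 12 months, unless the subject withdraws consent, dies or is lost to follow-up. The investigator's freedom over clinical care and over any repeat procedure is unchanged.

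The cost is a short amendment and some extra site effort to keep ill subjects in follow-up. No procedure is added beyond the schedule in Protocol 6.2.

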6.1.4.4. Enrollment time

Subjects will be considered successfully enrolled into the study after completion of the following process:

- Completion of the informed consent process and signing the ICF.
- Discretion by the investigator that the subject meets all inclusion criteria (including intra-procedure inclusion criteria) and does not meet any exclusion criteria.

No operation procedures related to the study (except for SOC) should be conducted prior to signing the ICF.

6.1.4.5. Expected overall duration of clinical trial and justification

The expected overall duration is about 31 months, including the time of EC, signing the contract, subject" enrollment and follow-up, data management and statistical analysis, and writing the clinical summary report.

6.1.4.6. Expected duration of participation of each subject

The duration of each subject's participation in the study is about 12 months according to the follow-up schedule specified in the protocol.

6.1.4.7. Number of subjects required for the clinical trial

A total of 123 non-roll-in subjects will be enrolled. Given at most 2 roll-in cases are planned per each investigator, a maximum number of 147 subjects (including both non-roll-in and roll-in subjects) will be enrolled.

See Section 7.2 "Calculation of Sample Size" for the basis for selecting such sample size.

6.1.4.8. Subject Enrollment Disposition

- Enrolled Subjects: Patients who sign the ICF and meet all eligibility criteria.
- Excluded Subjects: Subjects who are enrolled but never undergo insertion of the study catheter. Excluded subjects will be subjected to safety event reporting between ICF signature and date of exclusion. Enrolled Subjects found to be ineligible prior to insertion of the catheter are also considered as excluded.

- **Evaluable Subjects:** All enrolled subjects who have the study catheter inserted.
- **Discontinued Subjects:** Evaluable subjects but do not undergo ablation (i.e., no energy is delivered with the study catheter).
 - Discontinued subjects will remain in follow-up for 3-months post catheter insertion.
 - If an SAE is reported for a discontinued subject, the subject will be followed until event resolution (with or without sequelae), stabilization, or until the event is adequately explained.
- **Lost to Follow-up Subjects:** Evaluable subjects of which contact is lost after most recent visit (despite 3 documented attempts to contact the subject).
- **Withdrawn / Early Termination Subjects:** Subjects who withdraw consent for study participation or are withdrawn by the investigator, are terminated from the study prior to completion of all follow-up visits.
- **Completed Subjects:** Enrolled subjects who have not been excluded, discontinued, withdrawn, terminated early, or lost-to-follow-up from the study prior to the final study visit.

6.1.5. Effectiveness evaluation method

6.1.5.1. Description on effectiveness parameters

[figure not shown]
1) Primary effectiveness endpoint:

- Long term effectiveness: Freedom ≥ 30 seconds from documented asymptomatic and symptomatic AF, AT, and AFL of unknown origin⁺ based on electrocardiographic data (ECG or 24h Holter) during the effectiveness evaluation period (91-365 days post index procedure). Additionally, if a subject meets any one of the following criteria, then the subject will be considered an effectiveness failure:
 - a) Failure to achieve acute procedural success. Acute procedural success is defined as confirmation of entrance block in clinically relevant PVs (all PVs except those that are silent and/or cannot be cannulated) after adenosine and/or isoproterenol challenge.
 - b) Greater ($>$) than 1 repeat ablations for AF, AT, and AFL of unknown origin in the blanking period or any repeat ablation or surgical treatment for AF, AT, and AFL of unknown origin during the effectiveness evaluation period.
 - c) Non-study catheter failure, including:

- Use of a non-study catheter (NSC) to treat pulmonary vein targets to achieve isolation of clinically relevant PVs (all PVs except those that are silent and/or cannot be canulated) and/or to ablate left atrial non-PV AF targets during the index procedure

- Use of a non-study catheter to treat pulmonary vein targets to achieve isolation of clinically relevant PVs (all PVs except those that are silent and/or cannot be canulated) during repeat procedure in the blanking period

- Direct current or pharmacological cardioversion for AF, AT, and AFL of unknown origin during the effectiveness evaluation period.
- Continuous AF, AT, and AFL of unknown origin on a standard 12 or 15-lead ECG during the effectiveness evaluation period.
- A Class I and/or Class III AAD is prescribed for AF, AT, and AFL of unknown origin during effectiveness evaluation period, or end date of Class I and/or Class III AAD past day 90 post procedure.
- Oral amiodarone is prescribed post index ablation procedure

⁺AFL of unknown origin is defined as all AFL except those CTI dependent AFL as confirmed by 12 or 15-Lead electrocardiogram (ECG) or entrainment maneuvers in an EP study

2) Secondary effectiveness endpoint:

- Acute Procedural Success defined as confirmation of entrance block in all clinically relevant targeted PVs after adenosine/ isoproterenol challenge. Touching up with focal catheter will be considered as acute procedural failure.
- Acute reconnection identified by adenosine/isoproterenol challenge. Among all clinically relevant targeted PVs and by subject
- Rate of PV ablation by a non-study catheter (touch-up) among all

clinically relevant targeted PVs and by subject

- Rate of repeated ablation within the 12M FU period, including timing (blanking period or after blanking) and rate of PV reconnection

6.1.5.2. Selection of method and time to evaluate, record and analyze the effectiveness parameters

- 1) Long term effectiveness will be evaluated and recorded during effectiveness evaluation period (day 91 to day 365 post index procedure) by ECG and 24h Holter at 3 months, 6 months and 12 months follow-up points. Recurrence during blanking period (day 1 to day 90 post index procedure) is not considered as long term effectiveness failure.
- 2) Acute effectiveness will be evaluated and recorded at the end of procedure by the method of adenosine/isoproterenol challenge.
- 3) All the repeated ablations will be evaluated and recorded during the study.

For the analysis of the above endpoints, see Section 7.

6.1.6. Safety evaluation method

6.1.6.1. Description on safety parameters

Safety endpoints include

- 1) Procedure and device safety: The incidence of Primary Adverse Events (Aes) (within seven (7) days of the ablation procedure which uses investigational devices per protocol, including the initial and repeat procedures). PAEs include the following Adverse Events (Aes): Atrio-Esophageal Fistula*, Cardiac Tamponade**,***/ perforation**, PNP (permanent)[†], Pulmonary Vein Stenosis^{††}, Device or procedure related death^{†††}, Stroke/ CVA^{†,††}, Major Vascular Access Complication Bleeding, Thromboembolism, Myocardial Infarction, TIA, Pericarditis, Pulmonary Edema (Respiratory insufficiency), Heart Block, Vagal Nerve Injury/ Gastroparesis

** Atrio-esophageal fistula occurring up to 90 days post AF ablation process procedure will be considered a PAE.*

*** Cardiac Tamponade/Perforation occurring up to 30 days post AF ablation process procedure will be considered a PAE*

**** Hemodynamic compromise or instability is defined as Systolic BP < 80 mm Hg.*

[†] Absent phrenic nerve function as assessed by a sniff test. Refer to Table 4 for permanent phrenic nerve paralysis definition.

^{††} Pulmonary Vein Stenosis occurring anytime during the 12-month follow

up period will be considered a PAE.

+++ Device or procedure-related death anytime during or after the ablation procedure

[†]Non-focal global encephalopathy requires unequivocal evidence based upon neuroimaging studies to be reported as a stroke

^{††}Modified Rankin score assessments should be made by certified individuals.

- 2) Occurrence of Serious Adverse Events (SAEs) within 7 days (early-onset), 8-30 days (peri-procedural) and >30 days (late onset) of initial ablation procedure
- 3) **AEs and serious adverse events (SAEs).** Aes will be summarized, including the number of Aes and the number and percentage of subjects experiencing any Aes, the number of all SAEs and all related SAEs and number and percentage of subjects experiencing any SAEs.

6.1.6.2. Selection of method and time to evaluate, record and analyze the safety parameters

Records will be collected in the e-CRF at the discharge, Day, 1 Month, 3 Month, 6 Month and 12 Month follow-up visits respectively based on the investigator's notes, medical records and examination results. Aes will be collected after ICF signature. For the analysis of safety endpoints, see Section 7.

